7.1. Primary Efficacy Analysis

The estimand in the primary analysis for efficacy for each dose is the difference between treatments groups (each HP-5000 treatment group vs. placebo) in the change from Baseline to Week 4 in WOMAC pain score in all subjects as randomized, under the assumption that all randomized patients remain on their randomized treatment throughout the trial.

AD-ST-33.04 Effective date: 30-Jun-2017

Version 1.0 | Date 21-Oct-2019 | AD-PR-109.01 Effective date: 26-Jun-2017

Page 24 of 124

Statistical Analysis Plan,
 Sponsor Noven Pharmaceuticals, Inc.
 Protocol Number HP-5000-US-05
 [REDACTED]

The comparisons of interest are:

- HP-5000 [REDACTED] versus placebo
- HP-5000 [REDACTED] versus placebo

WOMAC scores obtained 24 hours after removal/detachment of the study medication or WOMAC scores obtained within 24 the subject used rescue medication will be excluded as outliers. Outliers will be defined *a priori* as (i) WOMAC scores obtained more than 24 hours after removal/detachment of double-blind study medication; or (ii) WOMAC scores obtained within 24 hours the subject used rescue medication.

The change from Baseline to Week 4 in the WOMAC pain score will be analyzed using a mixed model repeated measures (MMRM) analysis. The MMRM model will include change from baseline in WOMAC pain score as the repeated dependent variable, with treatment (HP-5000-[REDACTED], HP-5000-[REDACTED], and placebo), visit, treatment-by-visit interaction, and the baseline WOMAC pain score as covariates. The mean difference of change will be compared for each active treatment arm, and overall active against placebo. An unstructured covariance matrix will be assumed. If the unstructured matrix fails to converge, a series of other covariance structures will be tested (AR(1), Toeplitz, and Compound Symmetry). The covariance structure which converges with the lowest Akaike information criterion (AIC) score will be chosen and noted in the resulting table. The Kenward-Roger approximation for denominator degrees of freedom will be implemented, and the restricted maximum likelihood (REML) approach for estimation will be specified in the model code.

Below is example SAS code for conducting the MMRM analysis specified. Note, the macro wrapper used in different covariance structures is not shown below (specified with type option):

[figure not shown]
[figure not shown]
[figure not shown]
```
ods output lsmeans = lsmn1
      lsmestimates = lsmest1

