PMM is similar to MI but differs in that the strategy for missingness. Possible imputations do not come from the whole study cohort as mentioned above, but on the placebo group for the whole population. The idea is that discontinued subjects would be taking zero dose of the study drug after discontinuation and thus no longer exhibit any benefit from the treatment. In the above specified Step 3, instead of pulling from the entire study cohort, we will only draw from the placebo arm. The steps for this approach are detailed below:

1. Impute all non-monotone (intermittent) missing data using the MCMC method of PROC MI. Note that this imputation will sample data within each treatment group. SAS pseudo code is provided below.

```
PROC MI DATA=example seed = 6654 NIMPUTE = 20 OUT = outdata1;
  BY <treatment>;
  MCMC chain=multiple impute=monotone;
  VAR <treatment> <baseline> <V1> <V2> <V4>;
RUN;
```

AD-ST-33.04 Effective date: 30-Jun-2017

2. Using the imputed datasets from Step #1 that are now monotone missing (no intermittent missing data), a single call to PROC MI (including the MNAR statement) will be utilized to impute the monotone missing data.

SAS pseudo code is provided below. SAS accomplishes this iterative process in one step. Note that the treatment level 3 is the placebo treatment group:

```
PROC MI DATA=example seed = 2617 NIMPUTE = 20 OUT = outdata1;
  BY <time>;
  CLASS <treatment>;
  MONOTONE REG (<score> = <baseline> / details);
  MNAR MODEL (<score> / modelobs=(<treatment>=3));
  VAR <treatment> <baseline> <score>;
RUN;
```

3. When all missing data are imputed, PROC MIANALYZE will be used to combine the parameters from the analyses for inference.

Method 1 and 2 are MAR-based MI and pMI respectively. After MI, MMRM (same as primary analysis model) will be applied to imputed dataset.

Thus, there are two intercurrent events (discontinuation and use of rescue medication) and two imputation strategies (MAR-based MI and pMI). The following table provides more details how they will be used.

Summary of Analyses after intercurrent events				
Analysis	Method	Discontinuation	Rescue Med.	Comment
Primary	MMRM	NO	YES	
Sensitivity (1)	MMRM	pMI	YES	Method 2
Sensitivity (2)	MMRM	MAR-based MI	MAR-based MI	Method 1, Rescue Med. as a intercurrent event

Rules for handling missing or partial AE, concomitant medication data are described in Section [5.1.7](#).

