Note: ANCOVA = analysis of covariance, CI = confidence interval, LS = least-squares, SE = standard error, WOMAC = West Ontario and McMasters Universities Osteoarthritis Index. Treatment arms: HP-5000-[REDACTED] topical patch, HP-5000-[REDACTED] topical patch, and Placebo.

[1] Estimates are from an analysis of covariance model with change from baseline as the dependent variable. Terms for treatment, and baseline WOMAC Pain Score as covariates are included. The restricted maximum likelihood (REML) approach for estimation is used.

SOURCE: Listings xx.x.x, xx.x.x

T:\Noven\HP-5000-US-05\...\xxxxxx.sas run on DDMMYY at HH:MM for data extracted on DDMMYY, on SAS v9.4

{Programming Note: Repeat above layout for Week 2, and Week 4}

Statistical Analysis Plan,
Sponsor Noven Pharmaceuticals, Inc.
Protocol Number HP-5000-US-05
[REDACTED]

Table 14.2.1.5.1

MMRM Analysis of WOMAC Pain Score, Multiple Imputation by Study Visit, Discontinuation as Intercurrent Event
Full Analysis Set

{Programming Note: Repeat table 14.2.1.2.3 using MI imputed records for analyses. Add footnote referencing Section 7.1.1 implementation for MI}

Table 14.2.1.5.2

MMRM Analysis of WOMAC Pain Score, Multiple Imputation by Study Visit, Rescue Medication as Intercurrent Event
Full Analysis Set

{Programming Note: Repeat table 14.2.1.2.3 using MI imputed records for analyses. Add footnote referencing Section 7.1.1 implementation for MI}

Table 14.2.1.6.1

MMRM Analysis of WOMAC Pain Score, Pattern-Mixture Model by Study Visit, Discontinuation as Intercurrent Event
Full Analysis Set

{Programming Note: Repeat table 14.2.1.2.3 using PMM imputed records for analyses. Add footnote referencing Section 7.1.1 implementation for PMM}

Table 14.2.1.6.2

MMRM Analysis of WOMAC Pain Score, Pattern-Mixture Model by Study Visit, Rescue Medication as Intercurrent Event
Full Analysis Set

{Programming Note: Repeat table 14.2.1.2.3 using PMM imputed records for analyses. Add footnote referencing Section 7.1.1 implementation for PMM}

Statistical Analysis Plan,
 Sponsor Noven Pharmaceuticals, Inc.
 Protocol Number HP-5000-US-05
 [REDACTED]

Noven Pharmaceuticals, Inc.
 Protocol HP-5000-US-05

Page 1 of x
 FINAL

Table 14.2.1.7
 Responder Analysis of WOMAC Pain Score by Study Visit
 Full Analysis Set

Visit/Category Statistics [1]	HP-5000-[REDACTED] (N=xx) n (%)	HP-5000-[REDACTED] (N=xx) n (%)	Overall HP-5000 (N=xx) n (%)	Placebo (N=xx) n (%)
Week 1				
n	xx	xx	xx	xx
5% Improvement				

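### SAP 7.1.1 Method 2 assigns placebo-based imputation by missing-data pattern, not by discontinuation, so a Week 4 gap in an active-arm subject who has not discontinued is imputed as placebo

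*SAP*

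**What the plan says.** **Intended target.** SAP 7.1.1 gives the reason for Method 2: "The idea is that discontinued subjects would be taking zero dose of the study drug after discontinuation". In the summary table that closes 7.1.1, placebo-based imputation (pMI) appears only in the Discontinuation column, for Sensitivity (1). The Rescue Med. entry in that row is YES, which is not defined.

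**Operating steps.** Step 1: "Impute all non-monotone (intermittent) missing data using the MCMC method of PROC MI". On the data used: "Note that this imputation will sample data within each treatment group". Step 2: "a single call to PROC MI (including the MNAR statement) will be utilized to impute the monotone missing data". The Step 2 code contains "MNAR MODEL (<score> / modelobs=(<treatment>=3", where level 3 is placebo, and its regression line begins "MONOTONE REG (<score> = <baseline> / details". Neither the prose nor the code contains a discontinuation variable.

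**Scores set aside.** SAP 7.1 treats two kinds of WOMAC score as outliers: those taken more than 24 hours after patch removal or detachment, and "WOMAC scores obtained within 24 hours the subject used rescue medication". Neither is conditional on discontinuation. Protocol 13.4.3.1 excludes only scores taken more than 24 hours after study drug is discontinued and has no rescue rule.

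**Outputs.** SAP 14.2 plans two pattern-mixture tables. Table 14.2.1.6.1 is for discontinuation. Table 14.2.1.6.2 is titled "MMRM Analysis of WOMAC Pain Score, Pattern-Mixture Model by Study Visit, Rescue Medication as Intercurrent Event". Both shells refer back to 7.1.1, which describes no placebo-based imputation for rescue use.

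**The concern.** The zero-dose argument applies to subjects who have stopped treatment, but the algorithm looks only at the shape of the missing data. For a gap at the last visit the two do not coincide. A subject can finish the study on treatment and still lack a usable Week 4 score, and the SAP's own outlier rule may create such gaps.

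At stake is the interpretation of Sensitivity (1). It is presented as a test of one assumption about dropout. If it also strips drug effect from subjects who did not drop out, a weaker result cannot be attributed to dropout. The error runs against HP-5000, so it does not inflate false positives. The loss is in what the analysis can be said to show.

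**Working it through.** The plan gives no figure for this point. The check is to route each missing-data pattern through the two steps and then size the difference under stated assumptions.

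**1. Routing.** Post-baseline visits are Weeks 1, 2 and 4. A gap is intermittent if a later score is present, and monotone otherwise. Following the prose:

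| Week 1 / 2 / 4 | Imputed within arm (Step 1) | Imputed from placebo (Step 2) |
|---|---|---|
| seen / seen / missing | none | Week 4 |
| seen / missing / seen | Week 2 | none |
| missing / seen / seen | Week 1 | none |
| missing / missing / seen | Weeks 1, 2 | none |
| missing / seen / missing | Week 1 | Week 4 |
| seen / missing / missing | none | Weeks 2, 4 |
| all missing | none | Weeks 1, 2, 4 |

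Every pattern without Week 4 reaches the placebo model, whatever the reason. A rescue deletion at Week 1 or 2 with a later score present is imputed within arm. The same deletion at Week 4 is imputed from placebo. (The Step 2 pseudo-code reads the dataset called example, not the Step 1 output. Taken literally, intermittent gaps would go to placebo too. I follow the prose.)

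**2. Size with the baseline-only Step 2 code.** Let δ be the true Week 4 effect, d the share discontinuing, and r the share of the others with no usable Week 4 score. An active subject imputed from placebo given baseline contributes zero effect in expectation.

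- Selected by pattern: δ(1-d)(1-r)
- Selected by discontinuation, with other gaps imputed within arm: δ(1-d)
- Difference: δ·r(1-d)

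Neither d nor r is in the documents. Over assumed ranges of 5–20% for each, r(1-d) runs from 0.05 × 0.80 = 4% to 0.20 × 0.95 = 19% of the effect.

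The current effect size is redacted. An older protocol synopsis in the same file shows 0.32. That value gives 61.9% two-sided power for 75 v 150, not the stated 67%, which needs about 0.34, so 0.32 is illustrative only. With δ = 0.32 and d = r = 10%: 0.32 × 0.9 × 0.9 = 0.259 against 0.32 × 0.9 = 0.288.

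**3. Simulation, including earlier visits.** Method 2's prose adapts Method 1's Step 3, which conditions on previous outcomes. Week 1 and 2 scores carry part of the drug effect into the imputed value, so the loss shrinks. The table gives the percentage of the true effect retained at d = 10%, by pattern v by discontinuation. Settings: 75 v 150, effect 0.34 SD at each visit, assumed correlation 0.6, 20 imputations, 400 trials, Week 4 regression on treatment and baseline.

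| r | Formula | Step 2 on baseline only | Step 2 with Weeks 1 and 2 |
|---|---|---|---|
| 5% | 85.5 v 90 | 84.6 v 89.2 | 93.0 v 95.1 |
| 10% | 81 v 90 | 80.2 v 89.2 | 88.6 v 92.7 |
| 20% | 72 v 90 | 70.8 v 88.2 | 86.9 v 94.6 |

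A separate simulation used 1,500 replicates, effects of 0.20, 0.28 and 0.32 SD at Weeks 1, 2 and 4, and assumed correlations of 0.4–0.7. At d = r = 10% with earlier visits it gave 0.283 against 0.296 SD, with significance in 53% against 56% of trials. The Monte Carlo error is about 1.3 points on each percentage, so that last contrast is barely distinguishable.

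**The case against.** Much of the case on the other side stands.

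- **Off-patch scores.** A reader might infer that everyone affected was still wearing an active patch. The removal/detachment rule covers scores taken more than 24 hours off the patch, for which a zero-dose value is a reasonable fit. The mismatch concerns missed Week 4 visits and rescue deletions.
- **The undefined YES.** If YES for Sensitivity (1) means that rescue-affected scores are used, the rescue route closes for that analysis. Against this, the Primary row also says YES, while SAP 7.1 deletes those scores in the primary analysis. The two passages conflict, and that conflict does not prove misrouting. The missed-visit route remains under either reading.
- **Rarity.** Protocol 7.2 bans rescue within one calendar day before treatment-phase visits, and Protocol 10 asks for missed visits to be rescheduled. SAP 5.1.4 names premature discontinuation and missed intermediate assessments as the sources of missing data, so monotone pattern may have been meant as a proxy for dropout. The proxy fails at the final visit, but possibly for few subjects.
- **The two tables.** It is tempting to say that one algorithm cannot produce both pattern-mixture tables. It can, if different scores are set to missing when each input dataset is built. What is absent is the description.
- **Uniqueness.** Sensitivity (1) is not the only departure from within-arm MAR. The responder analysis in SAP 7.2.1 counts missing as non-response, and Method 1 draws on pooled drug and placebo records.
- **Benchmark.** The simulations delete scores at random and use a Week 4 regression, not the MMRM, so within-arm imputation is favoured by construction.

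**Conclusion.** The point holds as a mismatch between a stated target and a stated rule. Method 2 is meant for discontinued subjects. As written it also imputes from placebo the Week 4 score of an active-arm subject who has not discontinued but missed Visit 5, and of one whose score was deleted for rescue use if that deletion carries over. The direction is against HP-5000.

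The size is unknown. The upper figure, about r(1-d) of the effect, belongs to the baseline-only code, which is a separate matter. With earlier visits in the model the loss is clearly smaller: about 0.013 SD at assumed rates of 10%.

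A reader might infer that a robust result would be made to look fragile. The documents do not support that, because they give no discontinuation or deletion rate, and rescue deletions require a breach of the pre-visit ban. The change is worth making before unblinding because it is cheap and lets Sensitivity (1) answer its own question.

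**What to change.** In SAP 7.1.1:

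1. Add a discontinuation flag to Method 2, from the date of discontinuation or of last patch (both in Listing 16.2.1.2; Protocol 8.2.3 also records the last dose date).
2. Apply the MNAR placebo model only to visits after discontinuation, and use the same flag for Table 14.2.1.6.1.
3. Impute other missing or rescue-deleted scores, including Week 4, within arm under MAR.
4. State separately how scores deleted for patch removal or detachment are handled in subjects who have not discontinued.
5. Define YES and NO in the summary table and reconcile them with the deletion rule in 7.1.
6. Describe the rescue rule for Table 14.2.1.6.2, or delete that table. If a harsher placebo-based test of rescue use is wanted, it belongs there under its own label.

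The cost is some SAP wording and a few lines of code, with no new data. The downside is that MAR handling of rescue-related gaps may be somewhat favourable to active if rescue use tracks worse pain. The SAP should say so.

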7.2. Secondary Efficacy Analysis

The following secondary endpoints will be assessed using the FAS:

- WOMAC LK3.1 OA Index (pain) – change in pain score between Baseline and Week 1

and 2.

- *WOMAC LK3.1 OA Index (stiffness)* between Baseline and Week 1, Week 2, and Week 4.
- *WOMAC LK3.1 OA Index (physical function)* between Baseline and Week 1, Week 2, and Week 4.
- *WOMAC LK3.1 OA Index (composite score)* between Baseline and Week 1, Week 2, and Week 4.
- *Patient Global Assessment (PGA)* between Baseline and Week 4.
- *Patient Global Impression (PGI) of Change* between Week 1 and Week 4.
- *Pain intensity assessed on an 11-point numeric rating scale (NRS)* between Baseline and Week 1, Week 2, and Week 4.
- *Use of rescue medication* between Baseline and Week 1, Week 2, and Week 4.

All WOMAC LK3.1 OA Indices, PGA, PGI, and NRS secondary efficacy analyses will be performed similar to the primary analyses. An MMRM model will be used with change from baseline as the repeated dependent variable, with treatment (HP-5000-[REDACTED], HP-5000-[REDACTED], and placebo), visit, treatment-by-visit interaction, and the baseline assessment score as covariates.

The observed value and change from baseline each assessment score will also be summarized descriptively by visit using summary statistics in addition to the above noted model.

Figures of the Least Squared Means (LSM) of change from baseline will be plotted by treatment group and overall for the FAS for all by-visit outcomes. Within these figures, treatments will be distinguished by color and line type and jittered to prevent over-plotting at each visit. Each LS mean will include whiskers within a 95% confidence interval around the plotted value.

7.2.1. Responder Based on $\geq X\%$ Improvement¹¹ from Baseline

At each time point, subjects having X% or greater improvement from baseline in WOMAC pain score will be defined as “responders”. The percentage change will be defined as (Value at Week X – Baseline value) * 100 / (Baseline value). In other words, the responder indicator will be set to 1 if the percentage change is less than or equal to -X% and set to 0 if the percentage change is greater than -X% or missing. The different levels of required percent improvement from baseline are X=5% to 100% with 5% increments. These different thresholds for improvement will be summarized by visit for the FAS. Results will be reported by means of a graph with response threshold on the X-axis and proportion of responders in each treatment group on the Y-axis, this figure will only be completed for WOMAC pain. Corresponding data will be presented in a summary table. WOMAC stiffness, physical function, composite score, and NRS Pain improvement will be analysed similarly in separate tables.

7.2.2. Patient Global Impression of Change

The responders are defined as subjects achieving a score of

- 1: Very much improved or
- 2: Much improved or

Non-responders are defined as subjects achieving a score of

- 3: Minimally improved
- 4: No change or
- 5: Minimally worse or
- 6: Much worse or
- 7: Very much worse.

Subjects achieving a score of 0: Not assessed will be considered as missing data.

The proportion of PGI responders and non-responders will be summarized by visit. Treatment comparisons will be made using a logit model with treatment effect as the only term in the model analyzing the proportion of PGI responders. For each comparison, an estimate of the odds ratio, corresponding Wald 95% confidence interval and p-value will be presented. [Appendix A](#) contains example code constructed to complete the analyses. A plot showing the least square mean observed value by visit will also be presented.

7.2.3. Patient Global Assessment

The responders are defined as subjects achieving a score of

- 0: Very Good or
- 1: Good.

Non-responders are defined as subjects achieving a score of

- 2: Moderate or
- 3: Poor or
- 4: Very Poor.

Subjects not assessed will be considered as missing data.

The proportion of PGA responders and non-responders will be summarized by visit. Treatment comparisons will be made using a logit model as described in Section [7.2.2](#) adding PGA baseline as the covariate. This model will present an estimate of the odds ratio, Wald 95% confidence interval, and p-value.

7.2.4. Use of rescue medication

The proportion of subjects using rescue medication will be summarized by frequency and percentage by treatment and overall. As described in Section [7.2.2](#), a logit model will be employed similarly to compare treatments against placebo. This model will not contain any

baseline covariates but will present an estimate of the odds ratio, Wald 95% confidence interval, and p-value for use of rescue medication.

A by-subject listing of all efficacy assessments collected will be presented.

8. Safety and Tolerability Analysis

Safety will be evaluated from reported AEs, changes in clinical laboratory values, changes in vital signs, electrocardiogram (ECG), physical examination results, and dermal safety. No formal inferential analyses will be conducted for safety outcomes, unless otherwise noted. Unless otherwise specified, all safety analyses will be conducted on the Safety Analysis Set.

8.1. Adverse Events

All adverse events collected are treatment-emergent adverse events (TEAEs) since only AEs after treatment start are collected. All AEs, and SAEs will be coded using the MedDRA version 19.0 thesaurus.

The frequency and percentage of subjects reporting AEs, grouped by MedDRA system organ class and preferred term, will be tabulated by severity and treatment group for the SAF. Such summaries will be displayed for AEs, SAEs, AEs by relationship to study drug, and AEs by severity.

In the case of multiple occurrences of the same AE within the same subject, each subject will only be counted once for each preferred term. In the summaries showing severity and relationship to study medication the event with the maximum severity or strongest relationship will be reported. If a particular event is missing the severity and/or relationship, then the strongest possible severity or relationship will be assumed for analysis (severity = severe, relationship = definitely related).

Missing and partially missing AE start and/or stop dates will be imputed for the purpose of statistical analysis, according to the specifications described in Section [5.1.8](#).

In the AE data listings, all AEs will be displayed.

8.1.1. Adverse Events Leading to Withdrawal

A summary of incidence rates (frequencies and percentages) of AEs leading to withdrawal of study drug, by treatment group, SOC, and preferred term will be prepared.

A data listing of AEs leading to withdrawal of study drug will also be provided, displaying details of the event(s) captured on the CRF.

8.1.2. Deaths and Serious Adverse Events

Any deaths that occur during the study will be listed.

Statistical Analysis Plan,
Sponsor Noven Pharmaceuticals, Inc.
Protocol Number HP-5000-US-05
[REDACTED]

Serious adverse events will be listed and also tabulated by system organ class and preferred term and presented by treatment.

8.2. Clinical Laboratory Evaluations

Descriptive summaries of actual (absolute) values and changes from baseline will be presented for each clinical laboratory analyte by treatment group and overall at each visit.

The number of subjects with clinical laboratory values below, within, or above the normal range by time point will be tabulated for each clinical laboratory analyte by treatment group and overall. These shift tables will tabulate the number and proportion of subjects from baseline to post-baseline categories of low, normal or high.

By-subject listings of laboratory analytes will be presented. Any out-of-range values that are identified by the investigator as being clinically significant will be shown on this listing.

